### 7.2 Statistical methods

All evaluable patients will be included in calculating the 6-month PFS rate for the study along with corresponding 95% binomial confidence intervals (assuming the number of patients who are progression-free and alive at 6 months is binomially distributed). The numerator will be the number of patients at 6-months from enrollment who have either a complete response, a partial response, or stable disease (i.e. have not progressed) on re-staging imaging and who are alive. The denominator will be the number of patients on trial who received ipilimumab and SABR.

In addition, several secondary endpoints will be evaluated in these subjects:

- **Toxicity and Tolerability.** Frequency and severity of adverse events and tolerability of the regimen in each of the patient groups will be collected and summarized by descriptive statistics. As per NCI CTCAE v4.0, the term toxicity is defined as adverse events that are classified as either possibly, probably, or definitely related to study treatment. The maximum grade for each type of toxicity will be recorded for each patient, and frequency tables will be reviewed to determine toxicity patterns. In addition, we will review all adverse event data that

is graded as 3, 4, or 5 and classified as either “unrelated” or “unlikely to be related” to study treatment in the event of an actual relationship developing. The incidence of severe (grade 3+) adverse events or toxicities will be described. We will also assess tolerability of the regimens through assessing the number of patients who required dose modifications and/or dose delays. In addition, we will also capture the proportion of patients who go off treatment due to adverse reactions or even those who refuse further treatment for lesser toxicities that inhibit their willingness to continue participation on the trial. These tolerability measures will be assessed within each of the treatment arms and we will explore differences in these measures between the arms. All patients who have received at least one dose of any of the therapeutic agents in a treatment arm will be evaluable for toxicity and tolerability.

- **Overall response.** All evaluable patients (i.e. eligible patients who have received at least two doses of ipilimumab and SABR) will be assessed in terms of their best response to therapy by both mWHO and irRC. Those who achieve a partial response (PR) or complete response (CR) will be considered responses and the overall response rate will be calculated as the number of PRs and CRs divided by the total number of evaluable patients. Best overall response rate will be reported taking into account all post-treatment imaging.
- **Overall survival and progression-free survival as continuous time-to-event outcomes.** All evaluable patients will be used for this analysis. Kaplan-Meier curves will be used to estimate overall and progression-free survival. Each of these variables is measured from the date of study registration to the date of event (i.e., death or disease progression). In the case of the overall survival endpoint the date of last follow-up is to be used if no event has occurred at their last evaluation. In the case of the progression-free survival endpoint the date of last tumor assessment is to be used if no event has occurred at their last evaluation.
- **Correlative markers:** Several correlative markers will be explored in this trial in relation to clinical outcomes of interest, and in particular in relation to the primary endpoint of 6-month PFS rate. Given the limited overall sample size as well as the relatively limited expected proportion of patients who are progression-free and alive at 6 months, these analyses will be largely exploratory and hypothesis-generating in nature. Markers will be summarized univariately in a quantitative manner and also summarized by clinical outcome group (e.g. prog-free and alive at 6 months vs. not). Graphical analyses will be largely used to assess potential patterns and relationships; e.g. side-by-side boxplots to assess differences in continuous marker levels between those with vs. without the clinical improvement. We may also explore changes in these markers in relation to baseline, with clinical outcome incorporated through use of different plotting characters. Overall, hypothesis testing will largely be avoided given the sample size limitations but we will still obtain important preliminary data that can inform future studies and help better understand the mechanisms of this treatment regimen in this patient population.

*Statistical and Data Analysis:*

Assistance in statistical analysis will be provided by the Center for Biostatistics for The Ohio State University Comprehensive Cancer Center.

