### **3.2 Primary Study Endpoints**

- Rate of progression-free survival of ipilimumab and SABR in patients with oligometastatic melanoma as measured from the time of study enrollment until the first documented date of disease progression by mWHO criteria

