## **6.10 Definition of Efficacy Assessments**

- Rate of progression-free survival of ipilimumab and SABR in patients with oligometastatic melanoma as measured from the time of study enrollment until the first documented date of disease progression by both mWHO and irRC criteria.
- Frequency of grade 3 and grade 4 toxicities according to CTCAE (Common Toxicity Criteria for Adverse Events) version 4
- Frequency of objective response rate, defined as complete response + partial response, measured by mWHO criteria based on radiographic response rate will be determined based on re-staging CT of the chest, abdomen and pelvis
- Frequency of objective response rate, defined using the immune related response criteria (irRC) based on radiographic response rate will be determined based on re-staging CT of the chest, abdomen and pelvis
- Rate of local failure, as measured from the time of study enrollment until the first documented date of failure within the irradiated field
- Rate of overall survival, as measured from the time of study enrollment until the time of death

Biopsy, clinical evidence and radiographic evidence are all acceptable and will be used to document progression.

Overall survival: will be calculated as the time from entry on the study until the time of death.

Re-staging imaging with contrast-enhanced CT or MRI of the chest, abdomen, and pelvis will be performed before treatment, prior to 3rd ipilimumab infusion, 4 weeks after the final ipilimumab infusion (week 14 if there are no interruptions), and every 3 months for the first 2 years, then every 6 months during years 2-5.

The first re-staging scans after the week 14 imaging will be done at the 6 months from enrollment time point so that the endpoint of 6 month progression-free survival can be assessed.

All patients that have been treated on protocol with SABR and ipilimumab will have re-staging imaging even if they were taken off of protocol for adverse events after the SABR. Patients who do not have SABR due to adverse events from the first 2 infusions of ipilimumab are not required to complete re-staging imaging.

Patients who meet the criteria for Complete Response or Partial Response will have a re-imaging 4-weeks later to confirm the response.

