**Determination of Overall Response Using mWHO**

Overall Response (OR) is determined as the combination of assessments of *index* and *non-index* lesions using the following criteria:

Index Assessment	Lesion	Non-Index Lesion Assessment	New Lesions	Overall Response
CR		CR	No	CR
CR		SD	No	PR
PR		CR or SD	No	PR
SD		CR or SD	No	SD
PD		Any	Yes or No	PD
Any		PD	Yes or No	PD
Any		Any	Yes	PD

Best OR is the best confirmed response designation over the study as a whole, recorded between the date of first dose until the last tumor assessment for the individual patient in the study. The assessment of response at 12 weeks has particular emphasis due to the mechanism of action of ipilimumab inducing immune responses as basis for clinical responses. For the assessment of best OR, all available assessments per patient are considered. CR or PR determinations included in the best OR assessment must be confirmed by a second (confirmatory) evaluation meeting the criteria for response and performed no less than 4 weeks after the criteria for response are first met.

Patients will be assessed for efficacy by CT of chest, abdomen, and pelvis at baseline and every 6 weeks while on study and every 3 months thereafter, regardless of the location of known metastases. Similar methods of tumor assessment and similar techniques must be used to characterize each identified and reported lesion at screening and during subsequent tumor assessments. Imaging-based evaluation is preferred to clinical examination.

MRI of the brain will be used if brain metastases are being treated on study or if neurologic symptoms suggest concern for new or progressive disease within the brain.

If progressive disease is assessed based only on a new lesion(s) found on bone scans, additional imaging studies of the lesion(s) should be performed to confirm the malignant nature of the new findings on the bone scan. Increased intensity of uptake in previously abnormal areas on bone scans is not considered progressive disease, unless

the lesions seen on the correlative imaging studies performed of this area meet the criteria for progression. New areas of abnormal uptake on a bone scan represent progressive disease.

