**Response Endpoints**

Ipilimumab is expected to trigger immune-mediated responses, which require activation of the immune system prior to the observation of clinical responses. Such immune activation may take weeks to months to be evident. Some patients may have objective volume increase of tumor lesions or other disease parameters (based on study indication, ie, hematologic malignancies) within 12 weeks following the start of ipilimumab dosing. Such patients may not have had sufficient time to develop the required immune activation or, in some patients, tumor volume or other disease parameter increases may represent infiltration of lymphocytes into the original tumor or blood. In conventional studies, such tumor volume or relevant laboratory parameter increases during the first 12 weeks of the study would constitute PD and lead to discontinuation of imaging to detect response, thus disregarding the potential for subsequent immune-mediated clinical response.

Therefore, patients with tumor volume increase detected or lack of laboratory parameter response documentation prior to week 12 but without rapid clinical deterioration should continue to be treated with ipilimumab and clinically observed with a stringent imaging schedule to allow detection of a subsequent tumor response. This will improve the overall assessment of the clinical activity of ipilimumab and more likely

capture its true potential to induce clinical responses. Tumor assessments will be made using modified WHO criteria.

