## 7.0 STATISTICAL PLAN

### 7.1 Sample Size Determination

Overall, this study will require 32 evaluable patients. We estimate that we will accrue 1-2 patients per month; therefore, thus, the minimum study duration will be 16 months (2 accruals per month) and the maximum is 32 months (1 accrual per month for 32 patients).

Current literature and experience with ipilimumab in metastatic melanoma in this patient population shows that we can expect ipilimumab + SABR will not be considered promising in this patient population if at most 15% of patients are progression-free and alive at 6 months, because that is the expected 6 month PFS for ipilimumab alone. For this agent to be considered promising in this patient population, we would expect an improvement in the 6-month PFS rate to at least 35% with this regimen in this patient population. Constraining the Type I and II error rates to 10% each, the study design will require 32 evaluable patients to test these hypotheses regarding the 6-month PFS rate with ipilimumab when given in combination with the stereotactic ablative radiation therapy in this patient population. If we see at least 8 patients who have are alive and progression-free at 6 months after initiation of treatment out of the 32 evaluable patients, we will consider this sufficient evidence that this regimen has promising activity in this patient population. Otherwise, if 7 or fewer patients have are alive and progression-free at 6 months, we will consider this regimen to not be sufficiently active in this population of oligometastatic melanoma patients.

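### The rule for counting 6-month PFS successes in Section 7.2 does not say that an earlier mWHO progression disqualifies a patient, so it can be applied differently from the first-progression endpoint in Section 3.2

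*Combined protocol and SAP*

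**What the plan says.** Section 3.2 defines the primary endpoint as PFS from enrollment "until the first documented date of disease progression by mWHO criteria". Section 7.2 uses progression or death as the event for the Kaplan-Meier PFS curve.

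For the binomial primary rate, Section 7.2 gives the counting rule: "The numerator will be the number of patients at 6-months from enrollment who have either a complete response, a partial response, or stable disease". The rest of that sentence adds a parenthesis equating these categories with not having progressed, ties them to re-staging imaging, and requires the patient to be alive. It does not say whether mWHO or irRC applies, or whether progression on an earlier scan rules a patient out.

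Section 7.1 sets the hypotheses. The regimen is not promising "if at most 15% of patients are progression-free and alive at 6 months", and the target is "an improvement in the 6-month PFS rate to at least 35% with this regimen". Eight or more successes among 32 evaluable patients is called promising; seven or fewer is not.

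Section 6.10 describes the PFS event using mWHO and irRC together, and adds: "Biopsy, clinical evidence and radiographic evidence are all acceptable and will be used to document progression".

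**The concern.** In many trials it makes little difference whether one counts CR, PR or SD on the 6-month scan or no progression up to 6 months, because imaging stops at progression. This trial is built differently:

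- Under Section 6.10.2, mWHO progression needs no confirmation. A 25% rise in the sum of products over the smallest sum so far, or any new lesion, is enough.
- Section 6.10 places scans before the third infusion and at week 14, ahead of the 6-month scan.
- Section 3.1.2 recognises that stabilisation or response can follow early progression. It has patients with growing or new lesions complete induction, and keeps patients on study until both criteria sets show progression.
- The Response Endpoints text in 6.10.3 says that patients whose tumours grow early but who are not declining quickly "should continue to be treated with ipilimumab and clinically observed with a stringent imaging schedule to allow detection of a subsequent tumor response".

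Some patients may therefore have mWHO progression at week 7 or week 14 and still be scanned at 6 months. If their disease has regressed by then, two analysts could classify them differently under 7.2. The binomial rate and the Kaplan-Meier estimate at 6 months could then disagree for the same patients, and the go/no-go decision rests on a difference of one patient.

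**Working it through.** **Step 1: can the two readings diverge?** Take a hypothetical patient with a new lesion on the scan before infusion 3. By 6 months the lesion has gone, the index sum of products is 60% below baseline and non-index disease is stable.

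| Rule | Classification |
|---|---|
| Section 3.2, first mWHO progression | Event at the pre-infusion-3 scan; failure at 6 months |
| Section 7.2, Kaplan-Meier PFS | Event at the same date |
| Section 7.2 numerator, parenthesis read as a condition on the whole period | Failure |
| Section 7.2 numerator, parenthesis read as explaining the scan category | PR on the 6-month scan (60% exceeds the 50% threshold, no new lesion present); success |

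The divergence is confined to growth that regresses and new lesions that disappear. A new lesion still present at 6 months is PD in the mWHO table of Section 6.10.2, so that patient fails under every reading.

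**Step 2: reproduce the plan's design.** Section 7.1 states: "Constraining the Type I and II error rates to 10% each, the study design will require 32 evaluable patients". Inputs from 7.1 are n = 32, success if X ≥ 8, null rate 0.15 and target rate 0.35. With X ~ Binomial(32, p):

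- Type I error = P(X ≥ 8 | p = 0.15) = 0.0958
- Power = P(X ≥ 8 | p = 0.35) = 0.9182

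Both meet the 10% limits, and 32 with a cut-off of 8 is the smallest single-stage design that does so. The Study Summary calls the design two-stage Simon minimax. An exact search for that also gives n = 32 with the same final cut-off; for example, stopping if 2 or fewer of the first 17 succeed gives type I error 0.0906 and power 0.9053. No stated figure is in dispute.

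**Step 3: effect of one patient.** 7/32 = 21.9% is not promising; 8/32 = 25.0% is promising.

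**Step 4: effect on the error rate if scan status is counted.** Let d be the proportion of patients with mWHO progression before 6 months who read CR, PR or SD at 6 months. If true first-progression PFS is 0.15, the counted success rate is 0.15 + d. The documents give no value for d, so the range is assumed.

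| Reclassified patients expected per 32 | d | 0.15 + d | P(X ≥ 8) |
|---|---|---|---|
| 0 | 0 | 0.1500 | 0.096 |
| 1 | 1/32 = 0.03125 | 0.18125 | 0.212 |
| 2 | 2/32 = 0.0625 | 0.2125 | 0.367 |
| 3 | 3/32 = 0.09375 | 0.24375 | 0.535 |

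For scale, a true rate of 15% implies 0.85 × 32 = 27.2 expected failures, so the second row needs about one in 27 of them to be reclassified.

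**The case against.** The strongest reply is that 7.2 already means first progression. The parenthesis says so in ordinary English, since a patient with documented progression at week 7 has progressed. Section 7.2 calls the quantity the 6-month PFS rate, 7.1 counts patients alive and progression-free, and 3.2 defines the event. This carries real weight. A reader might infer that the plan definitely scores early progressors as successes, and the documents do not support that. The reply does not remove the gap, however. The parenthesis can also be read as explaining what CR, PR or SD on that scan signifies, and nothing in 7.2 looks back to earlier scans. The mWHO table is silent on carrying an earlier PD forward.

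The second reply is that the calculated inflation is hypothetical. That stands. The values of d are assumptions, and adding d to 15% presumes that the benchmark was measured by first progression on a comparable scan schedule. Section 7.1 takes the 15% from the pivotal phase III trial, which Section 1.2.1 describes as assessing tumours at weeks 12 and 24, with no mention of a scan near week 7. The benchmark's own progression rule cannot be seen. The table in step 4 therefore shows sensitivity and is not a demonstrated error rate.

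A reader might also infer that patients rescued by another drug after progression would count as successes. The documents largely close that route. Section 3.1.4 follows patients who stop for clinical progression and switch treatment only for date of death, and Section 5.6 bars non-study anticancer agents during the study.

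**Conclusion.** The gap is real but narrower than a flat contradiction. The counting rule for the primary decision names no criteria set and omits the condition that any earlier mWHO progression is final, in a trial that deliberately treats and images patients beyond such progression. The weight of the text favours first progression; the literal operational wording allows scan status.

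One reclassified patient is enough to reverse a 7/32 result. If one in 32 is reclassified on average, the chance of declaring a 15% regimen promising would be about 0.21 rather than 0.096. That figure rests on three assumptions: the reclassification rate, the scan-status reading, and a 15% benchmark that refers to first-progression PFS. The one-patient sensitivity needs no assumed rate, and is sufficient reason to settle the wording before outcomes are known.

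**What to change.** In Section 7.2, define a success as a patient alive at 6 months from enrollment with no documented mWHO progression at any assessment up to and including the 6-month scan. Apply the same progression rule to the binomial count and the Kaplan-Meier curve.

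In Section 6.10, reconcile two phrases with 3.2. State whether the joint mention of mWHO and irRC means two separately assessed endpoints or one combined event, and state whether clinical evidence alone counts as progression for the primary endpoint. Section 7.1 dates the 6 months from the start of treatment while 7.2 dates it from enrollment; use one origin in both.

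Report patients with early mWHO progression and later regression under the irRC secondary endpoint, so that this pattern is still described.

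The cost is a sentence or two in 7.2 and short clarifications in 6.10 and 7.1. No new data or scans are needed, and n = 32 and the cut-off of 8 do not change. The downside is that the primary rate may come out slightly lower than under a scan-status count.

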### 3.1.4 Follow-up

- Subjects who are no longer receiving ipilimumab because of unacceptable toxicity (refractory Grade > 3 immune-mediated adverse reactions) or due to investigator judgment are managed in follow-up. Efficacy assessments for these subjects during follow-up are as per the standard of care. Date of death is recorded.
- Subjects who discontinue ipilimumab treatments should be followed until death or the closure of the study (whichever is first).
- Subjects who are no longer receiving ipilimumab because of clinical progression and who have switched to alternative treatment are not followed formally except to record the date of death.

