***Immune-Related Best Overall Response Using irRC (irBOR)***

irBOR is the best confirmed irRC overall response over the study as a whole, recorded between the date of first dose until the last tumor assessment before subsequent therapy (except for local palliative radiotherapy for painful bone lesions) for the individual subject in the study. For the assessment of irBOR, all available assessments per subject are considered.

irCR or irPR determinations included in the irBOR assessment must be confirmed by a second (confirmatory) evaluation meeting the criteria for response and performed no less than 4 weeks after the criteria for response are first met.

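### The mWHO, irRC and section 7.2 rules give three different windows for best response, so scans taken after new anticancer therapy have no consistent treatment

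*Combined protocol and SAP*

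**What the plan says.** Three places in the combined protocol and SAP define the period over which best response is taken.

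- **Section 6.10.2 (overall response using mWHO):** best response is "recorded between the date of first dose until the last tumor assessment for the individual patient in the study". It adds: "For the assessment of best OR, all available assessments per patient are considered". Subsequent therapy is not mentioned.
- **Section 6.10.3 (irBOR):** best response is "recorded between the date of first dose until the last tumor assessment before subsequent therapy". Local palliative radiotherapy to painful bone lesions does not count as subsequent therapy.
- **Section 7.2 (overall response):** evaluable patients "will be assessed in terms of their best response to therapy by both mWHO and irRC". The same paragraph ends: "Best overall response rate will be reported taking into account all post-treatment imaging". It does not separate the two criteria and gives no cut-off.

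Section 3.1.4 governs who is still assessed after stopping ipilimumab. Patients who stop for clinical progression and "who have switched to alternative treatment are not followed formally except to record the date of death". For patients who stop for unacceptable toxicity or by investigator judgment, "Efficacy assessments for these subjects during follow-up are as per the standard of care". Section 6.10 adds that patients treated with SABR and ipilimumab continue re-staging even if taken off protocol for adverse events after SABR.

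**The concern.** Best response is meant to describe what SABR plus ipilimumab achieved. Once a patient starts another anticancer drug, later tumor shrinkage may be due to that drug. The irBOR definition guards against this; the mWHO definition does not. The analysis section, read literally, drops the guard for irRC as well.

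Two things are at stake. First, the mWHO response rate could include responses to other drugs. Second, the analyst cannot apply both 6.10.3 and 7.2 to a patient with scans on a new drug. The choice would then be made with the responses already visible.

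**Working it through.** **1. The windows side by side**

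| Section | Criterion | Start | End | Cut at new therapy |
|---|---|---|---|---|
| 6.10.2 | mWHO | first dose | last assessment in the study | none stated |
| 6.10.3 | irRC | first dose | last assessment before subsequent therapy | yes, bone palliation excepted |
| 7.2 | both named | post-treatment | all imaging | none stated |

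There are two mismatches: 6.10.2 against 6.10.3, and 7.2 against 6.10.3. The 7.2 sentence is not specific to mWHO, so the difference between the criteria rests on 6.10.2 and 6.10.3.

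**2. Can a scan on a new drug enter the data?**

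- *Switch after clinical progression:* section 3.1.4 ends formal follow-up apart from the date of death. This route is largely closed.
- *Stopped for toxicity or investigator judgment:* section 3.1.4 keeps efficacy assessments going.
- *Off protocol for adverse events after SABR:* section 6.10 keeps re-staging. Its schedule is every 3 months for 2 years, then every 6 months to year 5. These patients are in the response denominator, because 7.2 requires only eligibility, two ipilimumab doses and SABR.
- *Ban on other agents (section 5.6):* one sentence limits it to the period of ipilimumab treatment, while the list that follows says it applies during the study. Induction dosing ends at week 10 and imaging can run for years.

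The route is narrow but open. No section says how to treat a scan taken after a new drug starts.

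**3. Size per patient**

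Input: 32 evaluable patients (section 7.1), used as the response denominator (section 7.2).

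- One misattributed response: 1/32 = 3.1 points.
- Example: 5/32 = 15.6% (exact 95% CI 5.3% to 32.8%) becomes 6/32 = 18.8% (7.2% to 36.4%).

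**4. How many such patients?**

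The documents do not say. Two figures in them indicate the size of the toxicity pool:

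- Section 1.5.2 reports that 10% of patients discontinued ipilimumab for adverse reactions in the earlier phase 3 trial: 0.10 × 32 = 3.2 patients.
- Section 7.4 lets the trial continue with up to 4 of 18 patients having severe immune toxicity: 4/18 × 32 = 7.1 patients at the same rate.

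Only some of these would start another drug and be rescanned on it. Neither figure counts patients stopped by investigator judgment alone.

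As an assumption, not a forecast, let k patients be rescanned on a new drug, each with probability q of a response. The expected addition is k × q / 32.

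- Low: k = 2, q = 0.10 gives 0.2 responses, or 0.6 points.
- Middle: k = 4, q = 0.30 gives 1.2 responses, or 3.75 points.
- High: k = 8, q = 0.50 gives 4 responses, or 12.5 points.

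**5. Effect on the primary decision**

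The section 7.1 rule calls the regimen promising if at least 8 of 32 patients are alive and progression-free at 6 months. Exact binomial calculation gives P(X ≥ 8 | 32, 0.15) = 0.0958 and P(X ≥ 8 | 32, 0.35) = 0.918. Both meet the stated 10% error limits, so the plan's figure reproduces. Best response does not enter this rule, and changing its window leaves the sample size and both error rates as they are.

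**The case against.** The strongest reply is that the plan nowhere says scans after new therapy count. The mWHO window is confined to assessments in the study. Section 5.6 lists non-study anticancer agents as barred during the study, and section 5.9 allows no other systemic anti-melanoma therapy. On that reading an in-study scan is normally free of other drugs. Section 5.4 goes further: a patient for whom an adverse event makes continued treatment inadvisable must be withdrawn from the study, which could close the window. The 7.2 sentence may mean only that best response is not tied to one landmark scan. Finally, an mWHO response requires a 50% fall in the sum of products from baseline, no new lesions, and confirmation at least 4 weeks later.

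Much of this stands, and it rules out some stronger readings:

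- A reader might infer that the plan directs post-switch scans to be counted for mWHO. It does not. The problem is the word 'all' combined with the absence of a cut-off.
- A reader might infer that patients who progress and switch will inflate the rate. Section 3.1.4 removes them from formal tumor follow-up.
- A reader might infer a specific inflation, for example two patients lifting the 11% response rate quoted for ipilimumab in section 1.2 to about 17%. The count of two has no source. The 11% comes from a previously treated trial population, 71% of it stage M1c, rather than from this oligometastatic one.
- A reader might infer that the mWHO and irRC rates therefore cannot be compared. They already differ by design on new and non-index lesions (Appendix III). The differing window adds a further, avoidable difference.

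The reply does not remove the conflict. The ban in 5.6 has two different scopes. The withdrawal rule in 5.4 sits beside 3.1.4 and 6.10, which keep assessing patients who stopped for toxicity. The landmark reading of 7.2 is possible but is not what the sentence says.

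**Conclusion.** The inconsistency is real and can be seen from the text alone: mWHO has no cut at subsequent therapy, irBOR has one, and 7.2 overrides it if read literally. The risk of crediting another drug's response to SABR plus ipilimumab is confined mainly to patients who stop for toxicity or investigator judgment, or who come off protocol for adverse events after SABR, and who then start another drug and are scanned on it.

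Each misattributed response moves the rate by 3.1 points, given 32 evaluable patients. The total effect is unknown; the 0.6 to 12.5 point range rests on assumed numbers of patients and response probabilities. The endpoint is secondary and descriptive, and the 6-month PFS rule is untouched. The wording should be corrected before the data are analysed, but the point does not threaten the trial's main conclusion.

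**What to change.** - State one best-response window in 6.10.2, 6.10.3 and 7.2: from first dose to the last tumor assessment before subsequent anticancer therapy. Carry over the irBOR exception for local palliative radiotherapy to painful bone lesions.
- Record the start date of any new anticancer therapy, since the cut cannot be applied without it. The Appendix II schedule has a row for previous therapies but none for subsequent ones.
- If wanted, report the all-scans rate as a labelled sensitivity analysis.
- Reconcile the two scopes of the ban in 5.6, and the withdrawal rule in 5.4 with the continued assessment in 3.1.4 and 6.10, so that it is clear which assessments count as in the study.

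The window change costs protocol and SAP wording plus one data item. It changes neither the sample size nor the primary analysis.
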